4.2 Exclusion Criteria

- 1. Has biopsy-proven ocular, acral or mucosal melanoma
- 2. Has M1c or M1d disease
- 3. No more than one prior systemic anti-cancer regimen (monotherapy or combination) for management of melanoma. Additional details noted below:
 - a. Adjuvant anti-cancer therapy administered ≥ 6 months prior to the first injection of lerapolturev does NOT count as a line of treatment.
 - b. Patients with BRAF mutant melanoma may enroll if they have received ≤ 2 prior lines of systemic anti-cancer therapy only if one of those lines of therapy was a BRAF-targeted regimen (alone or in combination with MEK inhibitor).
 - c. A line of therapy is defined as a regimen in which at least 2 doses of systemic anti-cancer therapy (monotherapy or combination) was administered, and the regimen was discontinued because of progressive disease.

Confidential Page 58 of 109

- 4. Uncontrolled tumor-related pain. Participants requiring pain medication must be on a stable regimen at study entry
 - a. Symptomatic lesions amenable to palliative radiotherapy (eg, bone metastases or metastases causing nerve impingement) should be treated prior to enrollment. Patients should be recovered from the effects of radiation. There is no required minimum recovery period
 - b. Asymptomatic metastatic lesions that would likely cause functional deficits or intractable pain with further growth (eg, epidural metastasis that are not currently associated with spinal cord compression) should be considered for loco-regional therapy if appropriate prior to enrollment
- 5. Grade ≥2 pleural effusion, pericardial effusion, or ascites
- 6. Active or history of autoimmune disease or immune deficiency within previous 2 years, with the following exceptions:
 - a. History of autoimmune-related endocrinopathy (e.g. adrenal insufficiency, hypothyroidism, Type 1 diabetes mellitus, etc.) that is managed by hormone replacement therapy (e.g. hydrocortisone, thyroid hormone, insulin, etc.)
 - b. Eczema, psoriasis, or lichen simplex chronicus with dermatologic manifestations only (eg, patients with psoriatic arthritis are excluded), provided all of the following conditions are met:
 - i. Rash must cover <10% of body surface area
 - ii. Disease is well-controlled at baseline and requires only low-potency topical corticosteroids
 - iii. No occurrence of acute exacerbations of the underlying condition requiring psoralen plus ultraviolet A radiation, methotrexate, retinoids, biologic agents, oral calcineurin inhibitors, or high potency or oral corticosteroids within 12 months of Day 1
- 7. History of idiopathic pulmonary fibrosis, organizing pneumonia (eg, bronchiolitis obliterans), drug-induced or idiopathic pneumonitis, or evidence of active pneumonitis on screening chest computed tomography (CT) scan
 - a. History of radiation pneumonitis in the radiation field (fibrosis) is allowed
- 8. History of a positive HIV RNA test (HIV 1 or 2 RNA by PCR)
- 9. Known active hepatitis B virus (HBV) infection (chronic or acute)
 - NOTE: Participants with a negative HBsAg test and a positive total hepatitis
 B core antibody (HBcAb) test are allowed
- 10. Known active hepatitis C virus (HCV) infection
 - NOTE: History of a positive HCV antibody test, but negative HCV RNA test, is allowed
- 11. Active tuberculosis

Confidential Page 59 of 109

- 12. Significant cardiovascular disease, such as New York Heart Association Class II or greater cardiac disease, myocardial infarction, or cerebrovascular accident within 3 months of Day 1, unstable arrhythmia, or unstable angina
- 13. Has received prior systemic anti-cancer therapy including investigational agents within 4 weeks or 5 elimination half-lives—whichever is shorter—prior to treatment or has not recovered from all AEs due to previous therapies to ≤Grade 1 or baseline. Participants with ≤Grade 2 neuropathy are eligible
 - a. Note: Anti-PD-1/L1 within 4 weeks prior to Day 1 is allowed
 - If participant received major surgery, they must have recovered adequately from the toxicity and/or complications from the intervention prior to starting study treatment
- 14. History of other malignancy within 2 years prior to Day 1, with the exception of those with a negligible risk of metastasis or death (eg, resected cutaneous basal cell carcinoma, or other cancers with 5-year OS of >90%)
- 15. Severe infection within 4 weeks prior to Day 1, including, but not limited to, hospitalization for complications of infection, bacteremia, or severe pneumonia
 - a. Prophylactic antibiotics (eg, to prevent a urinary tract infection or chronic obstructive pulmonary disease exacerbation) are allowed
- 16. Prior allogeneic stem cell or solid organ transplantation
- 17. Treatment with a live, attenuated vaccine within 4 weeks prior to Day 1
- 18. Treatment with systemic immunosuppressive medication within 4 weeks prior to Day 1, with the following exceptions:
 - a. Participants who received acute, low-dose systemic immunosuppressant medication or a one-time pulse dose of systemic immunosuppressant medication (eg, 48 hours of corticosteroids for a contrast allergy) are eligible
 - Patients receiving mineralocorticoids (eg, fludrocortisone), or systemic prednisone equivalent corticosteroid doses of <10mg per day are eligible for the study
- 19. Known hypersensitivity to pembrolizumab, nivolumab, or any of the respective excipients
- 20. Requires therapeutic anticoagulation and cannot discontinue anticoagulation safely during the day prior, day of, and day after each lerapolturev injection
 - a. NOTE: Participants receiving anticoagulation with warfarin at the time of study entry are allowed if they can be transitioned to an alternative anticoagulant (eg, low molecular weight heparin or direct oral anticoagulants) prior to the first dose of lerapolturev. Anyone transitioned from warfarin to an oral anticoagulant prior to the first dose of lerapolturev should have an INR <1.5x upper limit of normal in order to participate. Antiplatelet agents (eg, aspirin, clopidogrel, etc.) are not considered anticoagulants for the purposes of this study (ie, are allowed)

Confidential Page 60 of 109

- 21. A pregnant or nursing female, or women of child-bearing potential and men who are sexually active and not willing/able to use medically acceptable forms of contraception starting from signed ICF through 150 days after last anti-PD-1 dose
- 22. History of human serum albumin allergy
- 23. History of neurological complications due to polio virus infection
- 24. History of agammaglobulinemia
- 25. Concurrent participation in a separate interventional clinical trial during this study
- 26. Any underlying medical condition for which, in the opinion of the investigator, participation would not be in the best interest of the participant (eg, compromises the participant's well-being) or that could prevent, limit, or confound protocol-specified assessments

4.3 Screen Failures

Screen failures are defined as participants who consent to participate in the clinical study but are not subsequently enrolled. A minimal set of screen failure information (demography, screen failure details, eligibility criteria, and any SAEs) will be collected to ensure transparent reporting.

Individuals who do not meet the criteria for participation in this study may be rescreened. Rescreening is at the discretion of the Investigator. Participants who are to be rescreened based on a laboratory exclusion are not required to reconsent. Otherwise, a new ICF is required before rescreening and the participant must be assigned a new participant number.

5 STUDY DRUG (LERAPOLTUREV, NIVOLUMAB OR PEMBROLIZUMAB)

5.1 Lerapolturev: Packaging, labeling and how supplied

Lerapolturev is a modified version of the serotype 1 live-attenuated (Sabin) PV vaccine (PV1S) and is classified as an oncolytic viral immunotherapeutic.

Lerapolturev is formulated in 50 mM sodium phosphate in 0.9% sodium chloride, pH 7.4 with 0.2% human serum albumin (HSA) in phosphate buffered saline (PBS). Lerapolturev is provided in sterile, single use glass vials with a flip off top containing approximately 0.5 mL of stock lerapolturev (2.24 x 10^9 TCID_{50}).

5.2 Preparation/Handling/Storage/Accountability

For complete lerapolturev storage, handling, and preparation instructions, please refer to the pharmacy manual. Lerapolturev preparation with Sponsor-supplied vehicle must occur in a biosafety cabinet or similarly contained environment in the institution's

Confidential Page 61 of 109

investigational pharmacy or equivalent. All handling of the study agent should occur under appropriate biosafety measures.

Any materials in contact with the study agent, eg, pipettes, vials, etc., should be disposed of as biological waste. The minimum final desired volume of the study agent for injection is 0.5 ml, and the maximum volume will be 3.0 ml. The final volume should be drawn into the intended delivery device(s) (See pharmacy manual for list of needles/syringes that are acceptable for lerapolturev administration).

5.3 Lerapolturev Dose, Schedule, and Administration

Dose: Lerapolturev should be administered at a fixed concentration of 5.33 x 10⁸ TCID₅₀/ml in accordance with the pharmacy manual (PM). Please refer to the PM for complete information regarding lerapolturev administration. The maximum volume injected at an individual treatment visit will be 3 ml, which is dependent on the number and size of injectable lesions. This corresponds to a maximum lerapolturev dose of 1.6 x 10⁹ TCID₅₀. The minimum injection volume is 0.5 ml (ie, minimum lerapolturev dose 2.67 x 10⁸ TCID₅₀). Up to 6 lesions may be injected at an individual treatment visit. It is possible that more than 1 syringe may be required to treat a single lesion, due to large lesion size. See Table 7 for recommended lerapolturev injection volumes. See Section 3.1.2 for instructions regarding lerapolturev dose for participants receiving the Q3/4W schedule of injections.

Confidential Page 62 of 109

Lesion Size (longest dimension [cm])	Maximum Injection Volume Per Lesion (ml)	Lerapolturev Concentration (TCID₅₀/ml)
≥ 5	3.0	
≥ 4 and < 5	2.0	
≥ 3 and < 4	1.5	5.33 x 10 ⁸
≥ 2 and < 3	1.0	
0.5 to <2.0	0.5	

Table 7. Recommended Lerapolturev Injection Volumes

Schedule: Participants will receive lerapolturev injections using the **QW** schedule which is defined as weekly x 7 followed by every 3 weeks (pembrolizumab) or every 4 weeks (nivolumab). See Section 3.1.1 for instructions of what injection schedule to use upon crossover. See Section 3.1.2 for instructions of what injection schedule to use for participants receiving the **Q3/4W** schedule.

Key Considerations Regarding Lerapolturev Injection:

- Where possible, at least one RECIST1.1/iRECIST target lesion should remain uninjected for as long as feasible while on study to facilitate the anti-tumor response assessment of non-injected target lesions.
- Participants with lesions known to be sensitive to intratumoral injection (ie, are painful, such as in transit lesions with limited subcutaneous tissue on the shin) may receive reduced injection volumes relative to the recommended volume for a given tumor size, per investigator's discretion, to manage tumor-related pain. However, the minimum allowable injection volume for a given lesion is 0.5 ml.
- Any lesion that is visible or palpable may be injected; lesions located in sites considered to be of more significant risk for complications from lerapolturev injection and associated inflammation (eg brain, lung, mediastinum, liver, pancreas, other visceral organs, lesions subjected to curative levels of radiation where radiation-associated toxicity has not healed, lesions encasing or immediately adjacent to major blood vessels including the carotid artery) are not to be injected in this study. Ultrasound may be used to better visualize the lesion during lerapolturev injection to optimize participant safety.
- Participants may stop receiving lerapolturev injections upon confirmation of CR or upon resolution of all injectable lesions (participants in Arm 2 should continue anti-PD-1 maintenance per manufacturer's prescribing instructions) and should be observed until progression/recurrence, at which point retreatment with lerapolturev is allowed. This process of injection, discontinuing injections and retreatment with injection may occur for a maximum of three times.
 - Participants receiving single-agent lerapolturev with a CR or complete resolution of all injectable disease (ie, other non-injectable disease persists) can crossover to Arm 2 upon progression. If upon progression, there are no

Confidential Page 63 of 109

injectable lesions, the participant should begin anti-PD-1 therapy monotherapy upon crossover.

- Lerapolturev injections should be administered concurrently with anti-PD-1 therapy during the "maintenance" schedule, (ie, Q3W for pembrolizumab and Q4W for nivolumab). Note that lerapolturev should be continued Q3W in the event pembrolizumab is administered on a Q6W cycle or Q4W in the event nivolumab is administered on a Q2W cycle.
- Where possible, participants should receive the same anti-PD-1 that they failed prior to study entry, administered in accordance with the respective package insert with respect to length of exposure and/or management (eg, dose delay or discontinuation) of irAEs.

Administration: Lerapolturev administration should be performed in accordance with the Pharmacy Manual. Anticoagulant and antiplatelet medications will be managed by the treating physician, per local institutional guidelines, to optimize the safety of intratumoral injection of lerapolturev.

5.4 Prior/Concomitant Therapy

There are no currently known contraindications or drug-drug interactions for lerapolturev (per the IB), pembrolizumab, or nivolumab as per FDA-approved package labeling. All medical conditions should be treated by the investigator per current standard of care. Participants may also receive medications for symptomatic relief (ie, analgesics, laxatives, anti-emetics).

 NOTE: Lerapolturev administration in combination with an anti-PD-L1 therapy is not allowed during this study

Medications the participant has received within 28 days of Day 1 until 30 days after the last dose of study drug(s) should be recorded in the eCRF. This includes, but is not limited to, prescription medications, over-the-counter medications, injected medications, natural/herbal remedies, biological products, blood products, imported drugs, or "street" drugs. Subsequent anticancer therapy should be collected until the end of study.

Prohibited Therapies:

Concomitant treatments that could prevent or mask potential AEs related to the investigational treatment or confound the assessment of its anti-tumor efficacy are not permitted, as far as the participant's safety is protected.

Administration of other systemic concomitant non-protocol anticancer therapies prior to progression is not permitted while on this study, with the exception of adjuvant endocrine therapy for breast cancer or prostate cancer defined as M0 disease or PSA persistence/recurrence without metastatic disease. Local treatment of isolated lesion(s) with palliative radiation therapy or surgery is permitted to control disease symptoms but

Confidential Page 64 of 109

not to aid in the response of the tumor. If the lesion(s) treated is being followed for evaluation by RECIST (target or nontarget lesion), then "not evaluable" should be reported in the eCRF for this lesion at subsequent disease assessments following palliative radiotherapy or surgery. Participants requiring palliative radiation may continue receiving study drug until documented disease progression (radiographic or clinical) if, in the Investigator's opinion, the participant is continuing to receive clinical benefit and they meet the requirements described in Section 6.2. However, for participants who have not had disease progression at the time of the need for palliative radiation therapy or surgery, the requirement for intervention will be regarded as disease progression in the study's analyses and will be entered as such in the eCRF.

The following medications are also not permitted:

- Non-protocol specified investigational drugs.
- Use of topical corticosteroids with occlusive dressings.
- Anticoagulant use the day prior to, day of and the day following lerapolturev injection. Warfarin use is not allowed at any time during study participation. Antiplatelet agents, such as aspirin, clopidogrel, etc., are not considered anticoagulants for the purposes of this study and are allowed.
- Live virus vaccines (beyond lerapolturev)
 - Examples of live virus vaccines include, but are not limited to, measles, mumps, rubella, varicella/zoster, yellow fever, rabies, and typhoid vaccine.
 - Seasonal influenza vaccines for injection are generally killed virus vaccines and are allowed; however, intranasal influenza vaccines (eg, FluMist[®]) are live attenuated vaccines and are not allowed.

COVID-19 Vaccination:

Vaccination against COVID-19 is allowed on study, provided the vaccine is not based on a live virus (eg, the Johnson and Johnson single-dose vaccine or AstraZeneca vaccine). While on study, it is recommended that participants vaccinated with non-live virus vaccines (eg, mRNA-based vaccines) receive the vaccine at least 14 days before or after lerapolturev administration, if possible. The COVID-19 vaccine should be given in an anatomic area as far as possible from melanoma lesions that were recently injected with lerapolturev or that are planned for future injection. Participants receiving a COVID-19 vaccine based on a live virus may begin Cycle 1, Day 1, once they are at least 4 weeks removed from vaccine administration.

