8.5 Statistical Analyses

The SAP will be developed and finalized before database lock and will describe the participant populations to be included in the analyses, and procedures for accounting for missing data. The statistical approach described in the SAP will supersede the statistical approach described here, in the event of discrepancy. This section is a summary of the planned statistical analyses for key endpoints of interest.

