Because lerapolturev is an immunotherapeutic administered by intratumoral injection, AESIs fall into 2 categories: (1) AEs related to lerapolturev administration (ie, injection site reaction [ISR]), and (2) AEs related to cytokine release syndrome [CRS] and immune effector cell-associated neurotoxicity syndrome [ICANS], which can occur when the body's immune cells release a bolus of inflammatory cytokines in response to an immunotherapy.

AESIs are collected through 90 days post last dose of study drug.

Immune-Related Adverse Events (irAEs)

Any adverse event affecting an organ system through an autoimmune or inflammatory mechanism, whereby the immune system is acting against normal tissue. The list of terms to identify irAEs is as

follows: (1) high level term (HLT): Colitis (excl infective); (2) HLT: Lower respiratory tract inflammatory and immunologic conditions; (3) HLT: Hepatocellular damage and hepatitis NEC; (4) HLT: Hypothalamic and pituitary disorders NEC; (5) HLT: Adrenal cortical hypofunctions; (6) HLT: Diabetes mellitus (incl subtypes); (7) HLT: Nephritis NEC; (8) HLT: Encephalitis NEC; (9) Preferred term (PT): Toxic epidermal necrolysis; (10) PT: Severe cutaneous adverse reaction; (11) PT: SJS-TEN overlap; (12) PT: Stevens-Johnson syndrome. Recommendations for study drug management in the event of an irAE are described in Protocol Section 5.5.

irAEs are collected through 90 days post last dose of study drug.

Concomitant Medications

Concomitant medications are those medications taken on or after the initiation of study drugs through 30 days post last dose of study drug. This definition includes medications started prior to initiation of study drugs and continuing concomitantly with study drugs.

Prior Medications

Prior medications are those medications taken and discontinued prior to initiation of study drugs.

Complete Response (CR)

A CR is defined by:

- disappearance of all target lesions AND
- disappearance of all non-target lesions AND
- all lymph nodes must be non-pathological in size (< 10 mm short axis) AND
- no appearance of new unequivocal lesions.

Partial Response (PR)

A PR is defined by:

- \geq 30% decrease in the sum of diameters of target lesions, taking as reference the baseline sum diameters AND
- non-CR / non-PD or not evaluated non-target lesions AND
- no appearance of new unequivocal lesions.

Stable Disease (SD)

Stable disease (SD) is defined by:

- non-PR / non-PD of target lesions AND

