- non-PD or not all evaluated of non-target lesions AND
- no appearance of new unequivocal lesions.

Progressive Disease (PD)

Progressive disease (PD) is defined by:

- \geq 20% increase in the sum of diameters of target lesions, taking as reference the smallest sum on study (this includes the baseline sum if that is the smallest on study) and an absolute increase of at least 5 mm OR
- unequivocal progression of non-target lesions OR
- appearance of one or more new lesions.

Duration of Response (DOR)

DOR is defined as time since a confirmed objective response (CR or PR) is first observed (ie, the scan date when the response originally occurred prior to confirmation) until unequivocal disease

progression (PD) or death, whichever occurs first. Participants will be censored at the date of the last imaging, if there is no date for PD or death.

Objective Response Rate (ORR)

ORR is defined as the proportion of participants achieving confirmed CR or confirmed PR.

Durable Response Rate (DRR)

DRR is defined as the proportion of participants with confirmed CR or confirmed PR lasting ≥ 6 months.

Overall Survival (OS)

OS is defined as time from start of treatment until death from any cause or last follow-up if participant is alive. Participants who are lost to follow-up will be censored at the last date of contact. The primary analysis will include the following subgroups:

- Participants who received lerapolturev monotherapy
- Participants who received lerapolturev + anti-PD-1
- Participants who crossed over from lerapolturev monotherapy to lerapolturev + anti-PD-1 from treatment group assignment until death from any cause or last follow-up, if participant is alive
- Participants who crossed over from lerapolturev monotherapy to lerapolturev + anti-PD-1 from time of crossover until death from any cause or last follow-up if participant is alive

Progression Free Survival (PFS)

PFS is defined as time (number of months) from start of treatment until date of documented radiologic disease progression or death due to any cause, whichever comes first. Participants not meeting this definition will be censored at the date of the last imaging. The primary analysis will include the following subgroups:

- Participants who received lerapolturev monotherapy
- Participants who received lerapolturev + anti-PD-1

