5.6.1.1. Statement of Estimand

The **population for the trial** is defined through appropriate inclusion/exclusion criteria to reflect the targeted participant population for approval. The analysis population is based on the efficacy population.

The **treatments** of interest are lerapolturev alone or lerapolturev + an FDA-approved anti-PD-1 therapy by dosing schedule.

The **variable** of interest for ORR is the binary response value for a participant.

The ability to evaluate treatment effect using the variables may be impacted by **intercurrent events** (ICEs). Death and use of additional cancer treatments may all impact the interpretation of treatment effect. For ORR, a composite strategy will be used to address intercurrent events (ICEs) of potential death, and start of additional cancer treatments, meaning occurrence of any of these events prior to a participant achieving CR or PR will mean the participant is considered a non-responder.

The **population level summary measures** are the ORR and associated confidence intervals in each treatment arm and lerapolturev dosing schedule.

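### Protocol 5.4 counts the need for palliative radiotherapy or surgery as progression, but the SAP does not carry the rule; PFS, DOR, DRR and DCR-6mo depend on which is programmed, and ORR may

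*Protocol*

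**What the plan says.** Protocol 5.4 permits local palliative radiotherapy or surgery for symptom control, and participants who need palliative radiation may stay on study drug. It sets two rules for the data. A treated target or non-target lesion is recorded as not evaluable from then on. In a participant who has not yet progressed, "the requirement for intervention will be regarded as disease progression", both in the analyses and in the eCRF entry.

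The SAP handles the same endpoints as follows.

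- **PD (3.2.6):** three lesion-based limbs (target growth, non-target progression, new lesions). Need for local treatment is not among them.
- **PFS (3.2.6):** runs "from start of treatment until date of documented radiologic disease progression or death due to any cause, whichever comes first". Otherwise, "Participants not meeting this definition will be censored at the date of the last imaging".
- **DOR (3.2.6):** runs to unequivocal PD or death, and is otherwise censored at last imaging.
- **PR (3.2.6):** the non-target limb reads "non-CR / non-PD or not evaluated non-target lesions AND".
- **ORR (5.6.1.1):** "a composite strategy will be used to address intercurrent events (ICEs) of potential death, and start of additional cancer treatments". Either event before CR or PR makes the participant a non-responder.
- **Section 7:** lists dropped exploratory analyses only.

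The PFS endpoint in Protocol 2.1 and the synopsis is also radiologic PD or death. Protocol 8.5 says: "The statistical approach described in the SAP will supersede the statistical approach described here, in the event of discrepancy".

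**The concern.** Protocol 5.4 is an analysis instruction as well as a conduct rule: it speaks of the study's analyses and of what is entered in the eCRF. The SAP neither repeats it nor says that it is dropped. The database can therefore hold a PD entry that the SAP's definition does not recognise, and a programmer must choose between that entry and a lesion-based derivation without guidance.

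The choice matters because treatment and scanning can continue after the intervention. If the SAP text is followed literally, stable disease, response and progression-free time can run on past a local treatment that removed or irradiated disease. The trial is open-label and the need for intervention is judged locally, so the rule should be settled before anyone sees which version is more favourable.

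**Working it through.** **Scan times.** Both schedules of assessments put imaging at Weeks 6 and 12, then every 12 weeks: Weeks 24, 36, 48. Times below count from start of treatment, and 6 months is taken as about 26 weeks. The intervention weeks are illustrative.

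**Endpoints with a direct conflict**

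- *PFS.* Intervention at Week 8, radiologic PD at Week 24. Protocol 5.4: event at 8 weeks. SAP text, and Protocol 2.1: event at 24 weeks. Difference: 24 − 8 = 16 weeks.
- *DOR and DRR.* First PR at Week 12, confirmed at Week 24, intervention at Week 30, PD on scan at Week 48. Protocol 5.4: 30 − 12 = 18 weeks, not durable. SAP text: 48 − 12 = 36 weeks, durable.
- *DCR-6mo.* Stable disease, intervention at Week 8, PD on scan at Week 36. Protocol 5.4: PD at Week 8, so not counted. SAP text: stable disease can be carried past 26 weeks and counted.

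**ORR, by timing of the intervention**

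- *Before any response.* Protocol 5.4: PD. SAP: non-responder if palliative local treatment is an additional cancer treatment, and the two then agree. If it is not, a PR remains possible where the treated lesion was non-target, because the PR definition tolerates unevaluated non-target lesions. A treated target lesion recorded as not evaluable limits that route.
- *Between first response and confirmation.* Protocol 5.4: PD, and SAP Table 4 turns PR followed by PD into SD, a non-responder. SAP text alone: a confirmed PR is possible, because 5.6.1.1 does not say whether achieving a response means the first or the confirmed one.
- *After confirmation.* ORR is the same; only DOR and DRR differ.

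**Size on ORR if a participant is reclassified.** Inputs from SAP 3.1 and 5.6.1.2: n = 15 in Arm 2 QW, exact two-sided 95% Clopper-Pearson interval, lower limit to exceed 10%. With x responders, the lower limit is the 0.025 quantile of Beta(x, n−x+1) and the upper limit the 0.975 quantile of Beta(x+1, n−x).

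- 5/15 = 33.3%: 11.8% to 61.6%. This reproduces the plan's figure.
- 4/15 = 26.7%: 7.8% to 55.1%. The criterion fails.
- One participant is 1/15 = 6.7 percentage points.

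**Sensitivity to an unknown rate.** The documents give no frequency, so the share f of true responders reclassified is an assumption. With a true ORR of 1/3, the chance of at least 5 of 15 is the binomial upper tail at p = (1/3)(1 − f):

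- f = 0: 0.596
- f = 5% (p = 0.317): 0.541
- f = 10% (p = 0.300): 0.485
- f = 20% (p = 0.267): 0.370

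**The case against.** A reader might infer that the SAP deletes the protocol's rule, so that someone treated at Week 8 whose target lesions then shrink is certainly a confirmed responder and the primary result is compromised. The documents do not support that.

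- The composite rule in SAP 5.6.1.1 may already make that participant a non-responder. The term additional cancer treatments is undefined. Some features suggest that palliation falls outside it: the schedules collect subsequent anticancer therapy only at end of treatment and in follow-up, and SAP 5.4 reports concomitant procedures separately. That leaves the question open; it does not establish misclassification.
- The precedence clause sits in Protocol 8.5 and concerns the statistical approach described there. The rule is in 5.4, and the SAP is silent on it, not contrary. The SAP introduction refers readers to the protocol for conduct and data collection, so the eCRF entry of PD still happens, and nothing says a lesion-based derivation overrides it.
- For PFS, the SAP takes its event from Protocol 2.1. The tension is first between Protocol 2.1 and 5.4.
- That 4/15 fails where 5/15 passes is true of any single reclassification. Eligibility also lowers the likely frequency: uncontrolled tumour pain is excluded, and symptomatic lesions amenable to palliative radiotherapy are to be treated before enrolment.
- PFS and DOR are descriptive Kaplan-Meier summaries with no formal hypothesis.

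All of this stands and limits the ORR point to a conditional one. It does not settle PFS, DOR, DRR or DCR-6mo, for which the SAP has no provision for the event while Protocol 5.4 has an explicit one.

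**Conclusion.** The conflict is real and unreconciled for PFS, DOR, DRR and DCR-6mo: following Protocol 5.4 and following the SAP text give different values for the same participant, 8 against 24 weeks of PFS in the example. The protocol is also inconsistent with itself on PFS.

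For ORR the effect arises only if palliative local treatment is not an additional cancer treatment, or if it falls between first response and confirmation without being caught. In those cases one participant could move the Arm 2 QW result across the 10% bar. How often this would happen cannot be judged from the documents; the 5%, 10% and 20% shares are illustrations. This should be fixed before analysis, but it is not evidence that the primary conclusion would be wrong.

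**What to change.** In SAP 3.2.6 and 5.6.1.1, carry over the Protocol 5.4 analysis rule:

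- Palliative radiotherapy or surgery to a tumour lesion before PD is a PFS and DOR event on the intervention date, and ends the duration of stable disease or response for DCR-6mo and DRR.
- For ORR, an intervention before a response is confirmed makes the participant a non-responder, in line with Table 4, where PR followed by PD gives SD.
- State that additional cancer treatments include these interventions, and that the eCRF PD entry made under Protocol 5.4 is used in the derivation.
- Align the PFS wording in Protocol 2.1 and the SAP with this event.

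If the sponsor means to keep radiologic PD only, list that departure from Protocol 5.4 in SAP Section 7. A sensitivity analysis that censors PFS and DOR at the last imaging before the intervention is optional.

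The cost is SAP wording, the matching protocol wording for PFS, and one derivation flag from data already collected (concomitant procedures and the eCRF PD entry). PFS, DOR and possibly ORR may come out slightly less favourable.
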